3. TAILOR STUDY – PROTOCOL FLOWCHART

4. INTRODUCTION

4.1. BACKGROUND

Wheezing in preschool children is a common and troublesome problem, leading to impaired quality of life and repeated admissions to hospital (1). Management hitherto has been largely on the basis of history, rather than biomarker driven, and bedevilled by meaningless questions such as 'At what age can you diagnose asthma?' (2,3). There is some merit in dividing these children into episodic viral wheeze (EVW, children who only wheeze with a usually clinically diagnosed viral respiratory tract infection) and multiple trigger wheeze (MTW, children who wheeze both with respiratory viral infections and with triggers such as exercise and allergen exposure between colds) (4), but such a distinction relies on accurate parental perception of symptoms (5). This is notoriously inaccurate, and for, example, when compared with a video questionnaire, it is clear that many sounds which are not the result of intrathoracic airway narrowing are described as wheeze by parents/carers.

The Lancet Asthma Commission has highlighted that 'asthma' is an umbrella term for a clinical syndrome comprising wheeze, chest tightness, breathlessness and sometimes increased cough (2). The focus has moved to defining so-called 'treatable traits', such as whether there is eosinophil airway inflammation, usually driven by the signature Type 2 cytokines Interleukin (IL) -4, -5, and -13, which are responsive to inhaled corticosteroids (ICS) (6,7). Nowhere is this concept of treatable traits more important than in preschool wheeze, wherein only a few children who wheeze have any evidence of allergic sensitisation or Type 2 inflammation. At age one year, even children with such severe symptoms as to merit bronchoscopy in a tertiary referral children's hospital had no evidence of any inflammation or airway remodelling (8). By 30 months of age, in another cross-sectional study, some but by no means all had evidence of eosinophil airway inflammation, reticular basement membrane thickening and airway smooth muscle hypertrophy and hyperplasia (9). Clinical experience reflects this diversity, and although atopic preschool wheezers are more likely to respond to ICS, as we have shown, many atopic wheezers do not have an eosinophil airway phenotype (10), and are thus unlikely to be ICS responsive. We have recently confirmed that there is a good correlation between bronchoalveolar lavage and peripheral blood eosinophil concentrations (11).

Another biomarker for eosinophil airway inflammation is exhaled nitric oxide (FeNO). In older children and adults, titrating ICS dose using FeNO has been shown to reduce asthma attacks and improve outcomes (12). The use of FeNO to guide management not been studied in pre-school children. Young children usually cannot perform the standard slow exhalation, but we have experience in measuring FeNO off-line by collecting tidally exhaled air, which is the technique we propose to use.

Allergic sensitisation as determined by skin prick tests, is another association of airway Type 2 inflammation in children, which has been used to predict response to ICS (13). Any biomarker which is of practical use in the management of preschool wheeze has to be able to provide an answer quickly and be available in primary care where most of these children are treated. A portable point of care measurement of peripheral blood eosinophil count from a finger prick blood sample will be carried out in a network of primary health care centres in and around Oxford (a finger prick being the sort of test done repeatedly at home for diabetic children to monitor insulin requirements) and exhaled nitric oxide measurements, meaning that both tests are practical by the above criteria.

Finally, it should be noted that atopy is not an 'all-or-nothing' phenomenon (14). We propose to perform exploratory, hypothesis generating analyses quantifying atopy by the sum of skin prick test wheals, to see if the predictive power of this test can be further improved.

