4.2. RATIONALE FOR CURRENT STUDY

Inhaled corticosteroids are effective treatment at all ages for patients with eosinophil airway disease, but have side-effects, including growth suppression, adrenal failure and increased susceptibility to respiratory infection. Only some children with preschool wheeze have airway eosinophilia, and thus benefit from inhaled corticosteroids, but these cannot be distinguished from the non-eosinophil phenotypes clinically. By using three simple point of care tests (blood eosinophil count, skin prick test to aeroallergens and FeNO) we aim to select out the subgroup of responders who will benefit, while avoiding exposing non-responders to potential side-effects.

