5. STUDY'S AIM AND OBJECTIVES

AIM: To obtain pilot data to test the hypothesis that aeroallergen sensitisation (confirmed by a wheal formation with a diameter ≥ 3 mm after a skin prick test is performed), FeNO (offline method) ≥ 10 ppb and a peripheral blood eosinophil count $\geq 300/\mu\text{l}$, alone or in combination, can predict future wheezing exacerbations in preschool children as well as response to treatment with inhaled corticosteroids, as a preliminary to a large, randomised controlled trial. Also, that these tests are acceptable to families.

OBJECTIVES:

- To recruit 100 preschool children with a history of wheeze, aged one to five years old, and determine atopic status, peripheral blood eosinophil count (point of care test) and FeNO (offline method).
- To evaluate the feasibility and acceptability of these tests
- To categorize the children according to the biomarkers tested and assess whether any or all, alone or in combination, predict future wheezing exacerbations as well as determine the clinical outcome over one year
- To obtain parents' and doctors' insights into whether the biomarkers mentioned above could be used in a future intervention study.

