10. END OF STUDY

The end of the study will be when the last of the 100 participants completes his follow-up period of 12 months with his/her last study visit. The anticipated finishing date is December 2023.

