11. STATISTICS AND DATA ANALYSIS

The statistical analysis of the project will be done by [name] in collaboration with [name] (University of Edinburgh) and the Asthma UK Centre for Applied Research (AUKCAR), the funder of the study. Statistical analyses will use the GraphPad PRISM software package. A normality test will be performed to assess normal (Gaussian) distribution (e.g., the Shapiro-Wilk test. If there is normal distribution, then parametric tests will be used, otherwise non-parametric tests. Level of significance is set as a p value <0.05. The tests that are currently planned to be used are:

- **Chi-Squared test (x²-test)**

This test allows assessing if a variable is similar between two or more groups or to test if two or more variables are related/dependent

- **Fisher's Exact test**

This test is used when chi-squared values are <5, usually with a small sample size.

- **Student t-test or Mann-Whitney test**

These tests are used for comparison between two study groups. The first is for normally distributed quantitative variables and the second for non-normally distributed quantitative variables.

Data and all appropriate documentation will be stored for a minimum of 10 years after the completion of the study, including the follow-up period.

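### As planned, the unadjusted marker comparisons cannot separate a marker that adds information from one that mirrors past attack frequency

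*Combined protocol and SAP*

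**What the plan says.** Section 4.1 (Background) opens the case for the tests by observing that "Management hitherto has been largely on the basis of history, rather than biomarker driven". It sees some value in the split between episodic viral and multiple-trigger wheeze, but warns that this depends on parents' perception of symptoms, which it regards as unreliable. Section 4.2 (Rationale) says of children with airway eosinophilia, who benefit from inhaled steroids, that "these cannot be distinguished from the non-eosinophil phenotypes clinically".

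Section 5 sets the objective: "categorize the children according to the biomarkers tested and assess whether any or all, alone or in combination, predict future wheezing exacerbations". The predictors named are the three markers; history is neither a predictor nor a comparator.

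Section 11 (Statistics and data analysis) introduces its list with "The tests that are currently planned to be used are" and gives chi-squared, Fisher's exact, and Student's t or Mann-Whitney tests. Of the last pair it says "These tests are used for comparison between two study groups". There is no regression, stratum or covariate. The one exploratory extension named, in Section 4.1, is the summed skin prick wheal size, which is also marker-only.

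**The concern.** Children who have had many attacks are plausibly more likely to have more. If a marker is commoner among them, it will be associated with future attacks even if it tells the clinician nothing beyond what the history already gives. The planned comparisons would count such a marker as predictive.

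Entry makes this more than theoretical. Section 7.2.1 admits children from primary care, the emergency department, outpatient clinics and record searches, with no minimum number of past attacks. Past severity is therefore likely to vary between children, and it may vary with marker status. A reader planning the later trial could take a crude marker association for information beyond history.

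**Working it through.** **1. Inputs from the documents.** Section 5: "To recruit 100 preschool children with a history of wheeze, aged one to five years old". Section 10: the study ends "when the last of the 100 participants completes his follow-up period of 12 months". Section 11: "Level of significance is set as a p value <0.05" (taken here as two-sided). No power, effect size, attack rate, marker prevalence or dropout is stated, so there is no figure of the plan's own to reproduce. Every rate below is an assumption.

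**2. Does history enter anywhere?** Not in Section 5, Section 6.1 or Section 11. The nearest visible item is TRACK question 5 (Appendix 3), on oral steroids over 12 months. It covers steroids only. Table 2 first schedules TRACK at month 3, when that window already includes follow-up. Table 3 of Appendix 1, which lists entry data, was not in the text available for this review.

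**3. How often would a pure proxy look predictive?** Let half of 100 children have frequent past attacks (h = 0.5). Let r1 and r0 be the attack risk in the year with and without that history, and m1 and m0 the proportion marker-positive in each group. The marker has no effect given history.

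- Share with frequent history among marker-positives: s1 = h·m1 / (h·m1 + (1−h)·m0). Among marker-negatives: s0 = h(1−m1) / (h(1−m1) + (1−h)(1−m0)).
- Attack risk in each marker group: s·r1 + (1−s)·r0.

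First scenario (r 60% v 30%, m 50% v 30%): s1 = 0.25/0.40 = 0.625 and s0 = 0.25/0.60 = 0.417. The risks are 0.4875 and 0.425. The apparent odds ratio is (0.4875/0.5125)/(0.425/0.575) = 1.29.

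| r1 v r0 | m1 v m0 | Apparent odds ratio | Unadjusted chi-squared, p<0.05 | Stratified by history |
|---|---|---|---|---|
| 60% v 30% | 50% v 30% | 1.29 | 9% | 5% |
| 70% v 30% | 50% v 25% | 1.535 | 18% | 5% |
| 70% v 30% | 60% v 20% | 1.96 | 39% | 5% |
| 60% v 30% | 40% v 40% | 1.00 | 5% | 5% |

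The percentages come from 4,000 simulated studies per row, with Monte Carlo error of about 1.5 points or less. The stratified test is Mantel-Haenszel. It holds 5% because the history variable here captures the whole of the child's attack tendency.

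**4. What if history is one year's count?** Assume 100 children, a mean of 1.5 attacks a year, log-normal attack tendency with squared coefficient of variation 1, and 30% marker-positive, the marker being linked only to past tendency. Fit negative binomial regression with and without log(previous count + 1).

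| Year-to-year correlation of tendency | Crude rate ratio | Adjusted rate ratio |
|---|---|---|
| 0.5 | 1.36 | 1.20 |
| 0.75 | 1.53 | 1.26 |
| 1.0 | 1.77 | 1.32 |

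With a weaker, logistic link between marker and tendency the pattern is the same but smaller: crude 1.18, 1.34 and 1.43; adjusted 1.08, 1.15 and 1.21. Adjustment moves the estimate towards 1 but does not reach it. The remainder is still there at 200,000 children, so it is not sampling noise: a single year's count measures tendency with error even if recall is perfect.

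**5. Precision.** Where marker and history are unrelated, adjustment cuts the variance of the marker effect by about 10%, 18% and 36% across the three correlations. In the linked scenarios the cuts are about 0%, 7% and 16%. These are gains over an unadjusted negative binomial model, not over the tests in Section 11. The standard error of the log rate ratio is about 0.27, so a 95% interval multiplies and divides the estimate by exp(1.96 × 0.27) = 1.70. Around 1.36 that gives 0.80 to 2.31.

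**6. Power of a history-stratified test.** In the first scenario of step 3, true odds ratios of 2, 3 and 4 given history would be detected in about 34%, 69% and 85% of studies.

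**The case against.** The strongest reply is that this is a feasibility study with no power claim. Section 4.3 gives its purpose as pilot data for power calculations, with feasibility and acceptability, and Section 5 does not claim value beyond history. A later trial stratified by marker would need attack rates within marker groups, and those are crude figures. This stands as a limit on the remedy: the crude comparison should stay, and the adjusted one is an exploratory addition. It does not remove the point, because prediction of attacks is a stated objective and attacks are the primary outcome.

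Several stronger readings are tempting, and the documents do not support them:

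- **That the protocol wants markers to replace history.** It criticises history-based care and seeks pilot data before a randomised trial. No passage says replace.
- **That Section 4.2 makes the same claim about attacks.** Its sentence concerns the eosinophilic, steroid-responsive phenotype. Adjusting attack rates for past attacks would not test it.
- **That history is not collected.** Table 3 was not available, so this cannot be alleged.
- **That the study can never address the question.** The tests are described as those currently planned. Section 13.5 also provides for consent to see medical notes, a possible source that does not depend on recall.
- **That the adjusted effect is the marker's added value.** Step 4 shows residual confounding in an example built so that the marker reflects past attack tendency alone.

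**Conclusion.** The point holds for the analysis as planned: every listed test is unadjusted, so a positive result would leave open whether the marker adds to history or stands in for it. Under the assumptions shown, a pure proxy would be declared predictive in about 9% to 39% of studies instead of 5%, or would show a crude rate ratio of about 1.4 to 1.8 (1.2 to 1.4 with the weaker link). If marker and history are unrelated, there is no such distortion.

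These magnitudes rest wholly on assumed rates and assumed links between marker and history. A precision gain of roughly 10% to 35% can be expected only if marker and history are unrelated; otherwise it is small or nil unless attack tendency is nearly constant from year to year. With 100 children the adjusted effect can be estimated, not confirmed.

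**What to change.** - **Entry data.** Confirm that Table 3 includes, or add, the number of unscheduled wheeze visits and oral-steroid courses in the 12 months before entry, and the symptom pattern. Take the counts from parents, or from medical notes under the access consent in Section 13.5.
- **Monthly question 3 (Appendix 4).** Ask for the number of visits. The present answers are frequency bands, and the lowest non-zero band merges one visit with two, so attacks cannot be counted for a rate ratio.
- **Section 11.** Add an exploratory regression, for example a negative binomial model with an offset for log follow-up time. Report each marker's effect with and without history (log of previous visits plus one, and symptom pattern), with confidence intervals. Check that the named software can fit it.
- **Interpretation.** State in advance that the adjusted figure is less confounded than the crude one and is not a measure of the marker's added value.

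The cost is a few entry questions, one reworded monthly item and one extra model. The drawbacks are imperfect parental recall, a symptom pattern that relies on the parental perception Section 4.1 distrusts, and wide intervals. If history is already recorded at entry, only question 3 and the analysis change.

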6. STUDY DESIGN

This is a pragmatic, observational study involving preschool children with wheeze aged one to five years old. All treatment and routine monitoring decisions will be at the discretion of their treating general practitioner (GP) or paediatrician (as per usual clinical practice), blinded to the study measurements. After clinical consultation and following submission of the electronic informed consent through the Qualtrics® platform (offered by Imperial College London), the parent/carer will be asked to give the contact details of the child's GP or paediatrician, who will be informed about child's participation in this study through a letter sent to his/her email along with the patient information sheet. The parent carer will be then shown a standard video questionnaire and will be asked to identify what respiratory sounds their children have been making. The child will be booked for the three biomarker tests [atopic sensitisation, blood eosinophil count and FeNO (off-line method)]. The tests will be carried out once and at a time of clinical stability. In this visit, a sample of the child's exhaled tidal breath will be collected in a suitable bag in duplicate for offline measurement of FeNO later on with chemiluminescence. Skin prick tests will be performed to: (a) house dust mite, (b) grass pollen, (c) tree pollen, (d) cat hair(e) dog hair, as well as normal saline and histamine and these will be applied on either the child's back, leg or arm. If the child has been prescribed antihistamines, we will ask for these to be withheld for 72 hours prior to skin prick testing. FeNO values (offline method) ≥ 10 ppb will indicate Type 2 inflammation and wheal diameter, measured with a specialised skin prick test ruler, ≥ 3 mm will indicate sensitisation to the applied aeroallergen. In addition, skin prick tests will allow the assessment of which aeroallergen is the most useful predictor of outcomes in preschool children. Finally, the peripheral blood eosinophil count will be measured from a finger prick blood sample, using the Haemocue machine, allowing a result in approximately 2 minutes. Values ≥ 300 cells/ μ l indicate Type 2 inflammation. All tests will normally take no more than one hour.

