All recruitment procedures will be in accord with the GCP, and parents/carers will be given detailed information regarding the study as well as all the time they need to understand it. Parents/guardians have at least 24 hours to consider participation. Recruitment will only commence after parents/carers have fully understood the project and submitted the electronic informed consent form through the Qualtrics® platform (offered by Imperial College London).

Child participants entering the study upon their parents' wish, will be fully screened by the Principal Investigator (PI) or someone else from the research team who is suitably qualified and delegated to do so, with the latter taking informed consent as well. After the electronic informed consent sheet is submitted, parents will be asked to provide the contact details of their child's GP or paediatrician, to inform him/her about the child's participation in this study through a letter sent by email along with this patient information sheet. In addition, we will ask them to provide some of the child's personal data (Appendix 1: Recruitment Plan, Table 3: The personal data that will be obtained by each individual participant). Children's full name, date of birth, gender, ethnicity as well as, their parent's full name, telephone number and email address will be added in the child's patient card. All other data obtained from the study will be added in the Case Report Form (CRF).

Follow-up: We will arrange for a short monthly electronic questionnaire to be sent by email to the parents/carers, in order to record on a monthly basis, the days their child was out of childcare, days the carer missed from work, unscheduled health care visits and use of rescue therapy or oral corticosteroids (including dosage) (Appendix 4: Monthly Questionnaire). In addition, we will record the children's TRACK™ score (Test for Respiratory and Asthma Control in Kids) (Appendix 3: TRACK™ score questionnaire) every 3 months, to assess wheeze control. The questionnaires will be made and sent through the Qualtrics® questionnaire platform (offered by Imperial College London). There will be review visits every 3 months, to evaluate their progression in person, but if not feasible, video calls will be arranged through Microsoft Teams. Correct use of spacers will be ensured after guiding parents on how to use them and will be done by their GP or paediatrician as well as from [name] who is a registered pharmacist in the UK.

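### Marker-versus-attack comparisons may be confounded by age, and no age adjustment is planned

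*Combined protocol and SAP*

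**What the plan says.** - **Population.** Section 5 sets the target: "To recruit 100 preschool children with a history of wheeze, aged one to five years old". They form one cohort, with no age strata.
- **Cut-offs.** Sections 5, 6 and 7.1 give one threshold per marker for every child: FeNO of at least 10 ppb, at least 300 blood eosinophils per microlitre, and a skin prick wheal of at least 3 "mm will indicate sensitisation to the applied aeroallergen".
- **Age gradient in the background.** Section 4.1 says that one-year-olds ill enough for bronchoscopy at a tertiary hospital showed no inflammation or remodelling, and continues: "By 30 months of age, in another cross-sectional study, some but by no means all had evidence of eosinophil airway inflammation". It also says that blood and lavage eosinophils correlate well and describes FeNO as a further marker of the same inflammation. The paragraph on skin prick tests links sensitisation to airway Type 2 inflammation.
- **Objective.** Section 5: "To categorize the children according to the biomarkers tested", and then assess whether the markers, singly or combined, predict later exacerbations.
- **Analysis.** Section 11 lists chi-squared, Fisher, t and Mann-Whitney tests. Of the last two it says: "These tests are used for comparison between two study groups". Age is not a covariate, stratum or subgroup anywhere in the visible text.
- **Age is known.** Sections 6 and 7.1 collect date of birth.

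**The concern.** If positivity rises with age and the cut-offs do not change with age, the marker-positive group will tend to be older than the marker-negative group. If attack frequency also differs by age, an unadjusted comparison mixes the marker's effect with that of age. A useless marker could then look protective or harmful, and a useful one could be hidden.

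This matters even when the aim is prediction. Section 4.2 justifies the tests on the ground that the phenotypes cannot be told apart clinically. Age costs nothing and every GP knows it, so the practical question is whether a finger prick, skin test or breath sample adds to it. The listed tests cannot answer that. Section 4.3 says the pilot data should inform power calculations for the definitive trial, so an age-mixed effect size could be carried forward.

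**Working it through.** **The plan's own figure.** The only relevant one is the target of 100 children. It comes with no effect size, event rate, power or precision, so there is nothing to reproduce.

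**Inputs from the documents.** Ages one to five, 100 children, 12 months' follow-up, fixed cut-offs, unadjusted tests, significance level 0.05 (two-sided assumed; the plan does not say).

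**Assumed inputs.** The age split, positivity by age, and attack frequency by age. The documents give none of these.

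**Step 1: attack rates, no marker effect within age.** Take two age groups of 50. With positivity p and yearly attack rate r, subscripts y (younger) and o (older):

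crude ratio = [(50·p_y·r_y + 50·p_o·r_o) / (50·p_y + 50·p_o)] ÷ [(50(1−p_y)r_y + 50(1−p_o)r_o) / (50(1−p_y) + 50(1−p_o))]

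| Positivity, y/o | Rate, y/o | Mean in positives | Mean in negatives | Crude ratio |
|---|---|---|---|---|
| 10%/50% | 3.0/1.5 | (15 + 37.5)/30 = 1.75 | (135 + 37.5)/70 = 2.46 | 0.71 |
| 10%/50% | 2.0/1.5 | (10 + 37.5)/30 = 1.58 | (90 + 37.5)/70 = 1.82 | 0.87 |
| 20%/50% | 3.0/1.5 | (30 + 37.5)/35 = 1.93 | (120 + 37.5)/65 = 2.42 | 0.80 |

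A true within-age ratio multiplies these. A true 1.5 appears as 1.07, 1.30 and 1.19; a true 2.0 appears as 1.42, 1.74 and 1.59.

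**Step 2: risk of any attack, no marker effect within age.** Take 40 younger and 60 older children with positivity 10%/40%. That gives 4 + 24 = 28 positives and 36 + 36 = 72 negatives. The rejection rate is Φ((d − 1.96·s0)/s1) + Φ((−d − 1.96·s0)/s1), where d is the absolute risk difference, s0 its pooled standard error and s1 its unpooled standard error.

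| Attack risk, y/o | Positives | Negatives | Crude RR | Rejection rate |
|---|---|---|---|---|
| 0.50/0.50 | 0.500 | 0.500 | 1.00 | 5.0% |
| 0.60/0.40 | 0.429 | 0.500 | 0.86 | 9.7% |
| 0.70/0.30 | (2.8 + 7.2)/28 = 0.357 | (25.2 + 10.8)/72 = 0.500 | 0.71 | 24.5% |
| 0.40/0.60 | (1.6 + 14.4)/28 = 0.571 | (14.4 + 21.6)/72 = 0.500 | 1.14 | 9.7% |

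If positivity is 30% in both age groups, the crude RR is 1.00 and rejection 5.0% at every risk pair tried. With the same 40/60 split, a weak gradient (positivity 20%/40%, risk 0.60/0.50) gives 0.96 and 5.5%. An extreme one (positivity 0%/40%, risk 0.70/0.30) gives 0.59 and 43.4%.

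**Step 3: a true within-age RR of 1.5, positivity 10%/40%.**
- Marker-negative risk 0.40 in both groups: crude RR 1.50, power 43.7%.
- Marker-negative risk 0.50/0.30: (3.0 + 10.8)/28 = 0.493 against (18 + 10.8)/72 = 0.400. Crude RR 1.23, power 13.6%.
- Marker-negative risk 0.60/0.30: (3.6 + 10.8)/28 = 0.514 against (21.6 + 10.8)/72 = 0.450. Crude RR 1.14, power 8.9%.

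**Step 4: stratifying by age (Mantel-Haenszel RR, expected counts).**
- Null case, risk 0.70/0.30: (2.8·36/40 + 7.2·36/60) ÷ (25.2·4/40 + 10.8·24/60) = 6.84/6.84 = 1.00, against a crude 0.71.
- True RR 1.5, risk 0.60/0.30: (3.6·36/40 + 10.8·36/60) ÷ (21.6·4/40 + 10.8·24/60) = 9.72/6.48 = 1.50, against a crude 1.14.

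**The case against.** **Both links are inferred.** A reader might take Section 4.1 to say that Type 2 inflammation is absent at one year. It does not: it reports bronchoscopy in one severe, tertiary-referred group and gives no FeNO, skin prick or blood eosinophil result at that age. It also notes that many atopic wheezers lack an eosinophilic airway phenotype, which weakens the inference for skin tests. A reader might also conclude that the comparison is confounded. That needs attack frequency to vary with age, and the documents do not address this. Both objections stand, and they limit the point to a possibility of unknown direction.

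**The documents' own evidence leans the other way.** In the trial described in Section 4.3, children with neither positive skin tests nor raised eosinophils seldom had attacks. That argues against expecting marker-negative children to have more attacks. It does not separate marker from age, so it does not answer the point.

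**Prediction is not causation.** A crude association is legitimate pilot information, and Section 11 describes its tests as those currently planned. This is fair. What remains is that added value beyond age cannot be shown. That the definitive trial would adopt the wrong marker is speculation.

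**Two further inferences fail.** Thirty months is the age reported for a cited study, not a threshold that the protocol sets. Nor can one infer that age is missing from the case report form because date of birth is on the patient card. Table 3 of Appendix 1, which lists the personal data collected, is not in the visible text, and age can be derived from date of birth in any case.

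**Conclusion.** The point holds as a missing safeguard, not as a demonstrated bias. The documents establish fixed cut-offs across ages one to five, a background that gives reason to expect positivity to rise with age, and an analysis that ignores age.

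The size is conditional. With no true marker effect, the Step 1 scenarios give crude ratios of 0.71 to 0.87 when younger children have more attacks. Weaker or stronger gradients move this towards 1 or further from it. If older children have more attacks the ratio exceeds 1. If either link is absent there is no bias. Every positivity and attack figure is an assumption. Because the direction is unknown, the crude result cannot be corrected by judgement afterwards, which is the reason to plan the adjustment now.

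**What to change.** In Section 11:

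1. Derive age in months at biomarker testing from the date of birth already collected. Age in months can be held in the analysis data without the date itself.
2. Prespecify one age band split, and report marker positivity and attacks within each band.
3. Report an age-adjusted marker-attack estimate alongside the crude one. Use Mantel-Haenszel by age band, or a logistic model for any attack with one age term. The logistic model gives an odds ratio, which can shift on adjustment even without confounding, so compare crude and adjusted results on the risk-ratio scale.
4. Use a count model only if actual visit numbers are recorded. Question 3 of the monthly questionnaire (Appendix 4) uses frequency bands, which give any attack or none but not a count.

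The cut-offs stay as they are and families supply nothing new. The cost is one derived variable, a short addition to Section 11 and one extra model term. With 100 children that is affordable, but precision within bands will be poor: the layout in Step 2 has only 4 marker-positive children in the younger band.
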